## Introduction

The PROVENT study aims to test the feasibility of a randomised controlled trial to examine the clinical effectiveness of aspirin and/or Vitamin D3 in preventing disease progression in men on active surveillance for low- to medium-risk prostate cancer. The main objective of this randomised feasibility trial is to demonstrate the acceptability of recruitment rates and the potential numbers required for a definitive trial. The study has a 3x2 factorial design, comparing a placebo to aspirin administered at low dose (100mg) or high dose (300mg), and placebo to Vitamin D3 at 4000IU.

## Sample size

Sample size calculations suggested that 800 men are needed for a future definitive randomised chemoprevention study of standard (300mg) or low dose (100mg) aspirin vs. placebo and/or Vitamin D3 vs. placebo in patients enrolled on an Active Surveillance programme for prostate cancer.

This feasibility trial aims to demonstrate the acceptability and viability of recruitment for this larger study. Data from this trial will be used to determine the number of centres required to enable the larger, 800 patient trial to fully recruit within 4 years. The sample size was chosen to examine acceptance rates and the time required to recruit 102 patients. We plan to recruit 102 patients over 18 months. If the true recruitment rate is 33.3%, approaching 300 individuals, and therefore recruiting ≥100, would achieve 89% power to show that the true recruitment rate is above 25% (using a two-sided binomial proportion test with a 0.05 significance level).

# Randomisation procedure

The randomisation will be by permuted block randomisation in order to achieve approximate balance across the 6 treatment groups. This randomisation scheme consists of a sequence of blocks such that each block contains a pre-specified number of treatment assignments in random order, for example each treatment occurring twice in a block. The purpose of this is so that the randomisation scheme is balanced at the completion of each block. PROVENT has 3x2 treatment combinations (a block of 6). However, there are two sizes of placebo aspirin to match the active drug: small (100mg size) and large (300mg size) providing an added complication, as this effectively produces eight possible combinations. To maintain the correct balance of drug and placebo, the PROVENT feasibility study will use two blocks of 6 to make a 'Superblock' of 12. In one block of 6 the placebo aspirin will be first small and then large, and in the other block they will be first large and then small. This ensures the correct number and size of placebo aspirin are dispensed, and that all 8 treatment combinations are represented in each superblock. Consequently, twice as many aspirin, as placebo aspirin tablets, are required for the trial.

# **Primary Endpoint**

The primary endpoint for this feasibility study is the rate of patient recruitment over a 12-month period which will be assessed through pre-screening logs and eligibility CRFs.

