# Analysis of primary endpoint

Patient recruitment will be defined as the proportion of eligible patients recruited from the total number of eligible patients. This will be reported with 95% CI calculated using a binomial test for proportions.

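### The SAP gives its only primary endpoint a 12-month window, plans recruitment over 18 months, and analyses a proportion with no window

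*SAP*

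**What the plan says.** Three sections of the SAP describe recruitment.

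- **Primary Endpoint:** the endpoint is "the rate of patient recruitment over a 12-month period", "which will be assessed through pre-screening logs and eligibility CRFs".
- **Sample size:** "We plan to recruit 102 patients over 18 months". The power statement is for a proportion: with a true rate of 33.3%, "approaching 300 individuals, and therefore recruiting ≥100, would achieve 89% power to show that the true recruitment rate is above 25" per cent, by a two-sided binomial test at the 0.05 level. The same section gives two further aims. One concerns pace: "The sample size was chosen to examine acceptance rates and the time required to recruit 102 patients". The other is that the data will be used to "determine the number of centres required to enable the larger, 800 patient trial to fully recruit within 4 years".
- **Analysis of primary endpoint:** recruitment is "the proportion of eligible patients recruited from the total number of eligible patients", and "This will be reported with 95% CI calculated using a binomial test for proportions". This section states no period.

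No section specifies an analysis of recruits per month, recruits per centre, or time to 102 recruits.

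**The concern.** Recruitment is the purpose of this feasibility trial, so its primary estimate should have one meaning. The word 'rate' can be read in two ways, and neither fits all three sections.

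- **A proportion**, as the Sample size and Analysis of primary endpoint sections use it. The 12-month window then conflicts with the 18-month recruitment plan. The analysis section does not say whether men assessed after month 12 count.
- **Accrual per 12 months.** The window is then only a unit of time, but the planned analysis is a proportion without a time unit. The stated endpoint is not analysed.

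The window decides which men enter the only primary result, and as written it could be chosen after the logs are seen. The stated power belongs to one definition only, the one in which all 300 men count. The number of centres also depends on pace, which the only specified recruitment analysis does not report.

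**Working it through.** **Inputs.** From Sample size: null proportion p0 = 0.25, alternative p1 = 1/3, n = 300, two-sided alpha 0.05, 102 recruits in 18 months, and 800 men in 4 years (48 months). From Primary Endpoint: 12 months.

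**1. Reproduce the 89%.** Normal approximation, with the null standard error setting the critical value:

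power = Φ{[(p1 − p0)√n − 1.96√(p0(1 − p0))] / √(p1(1 − p1))}

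n = 300: (0.0833 × 17.32 − 1.96 × 0.4330) / 0.4714 = (1.443 − 0.849) / 0.4714 = 1.26, so power is 89.6%.

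Exact binomial: the smallest count with upper-tail probability at or below 0.025 under p0 is 91 of 300 (tail 0.021). The chance of 91 or more under p1 is 87.8%. The arcsine approximation gives 88.9%. The SAP's 89% is right for its inputs.

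**2. Reading 'rate' as a proportion within 12 months (illustration).** The SAP does not say how approaches are spread over time. Assume an even spread over 18 months: 300 × 12/18 = 200 men.

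n = 200: (0.0833 × 14.14 − 0.849) / 0.4714 = (1.179 − 0.849) / 0.4714 = 0.70, so power is 75.8%.

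| Men counted | Exact (critical count) | Arcsine | Normal |
|---|---|---|---|
| 300 | 87.8% (91) | 88.9% | 89.6% |
| 200 | 73.2% (63) | 73.9% | 75.8% |

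Exact power is uneven near 200 because counts are discrete (69.9% at 198, 74.8% at 201), so 73-76% is a rough range.

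Effect on the expected estimate (exact 95% CI): 100/300 gives 33.3% (28.0-39.0%); 67/200 gives 33.5% (27.0-40.5%). The interval is wider, but both lower limits lie above 25%.

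**3. Reading 'rate' as accrual per 12 months.** The plan implies 102 × 12/18 = 68 recruits per 12 months. No specified analysis produces this figure.

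**4. What the proportion says about pace.** At 33.3%, 102 recruits come from 306 men; 102/306 has an exact 95% CI of 28.1-38.9% however long recruitment took. The definitive trial needs 800/48 = 16.67 recruits per month.

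| Time taken to recruit 102 | Recruits per month | Scale-up to 16.67 per month |
|---|---|---|
| 12 months | 102/12 = 8.50 | 1.96-fold |
| 18 months | 102/18 = 5.67 | 2.94-fold |

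The two periods named in the SAP give scale-ups that differ by 2.94/1.96 = 1.5-fold, while the proportion is the same.

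**The case against.** The strongest reply is that the inconsistency comes down to one phrase. The Sample size and Analysis of primary endpoint sections both treat recruitment as a proportion. An analysis with no stated window most naturally covers all recruitment, hence the planned 18 months. The 12-month phrase could also be an annualised unit. This stands in part: it narrows the conflict to the Primary Endpoint section. It does not remove it, because that section is where the endpoint is defined, the SAP never says the figure is annualised, and an annualised rate would still have no analysis.

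Four stronger readings are tempting, and the SAP does not support them.

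- *The power is miscalculated.* It is not; 89% is reproduced.
- *The denominator is open as well.* The analysis section fixes it as all eligible men. The mismatch with the 300 men approached may be only wording, since pre-screening logs and eligibility CRFs are compatible with men being screened before they are approached. The SAP gives no figure for eligible men not approached or approached men found ineligible, so no size can be put on a difference.
- *The number of centres cannot be obtained.* The Sample size section relies on data from the trial, not on the proportion alone, and time to 102 recruits will be observed. The gap is that no accrual analysis is specified.
- *A wrong go/no-go decision would follow.* The SAP plans an estimate with a confidence interval and states no decision rule beyond the power sentence. The expected 12-month result would still exclude 25%.

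**Conclusion.** The concern holds as an inconsistency in the definition of the only primary endpoint. Either the 12-month window conflicts with the 18-month plan, or accrual is meant and the endpoint has no analysis. The consequence is an ambiguous primary estimate and a power statement that is not tied to it.

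The size depends on the reading. For a proportion limited to 12 months, power falls from 89% to roughly 73-76%; this rests on the assumption that approaches are even over 18 months. For accrual, the planned 68 recruits per 12 months has no analysis behind it. For planning centres, the 12- versus 18-month difference alone changes the required scale-up 1.5-fold. The textual conflict itself needs no assumption.

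**What to change.** 1. In Sample size, Primary Endpoint and Analysis of primary endpoint, state whether the rate is a proportion or accrual per unit time, and use one window. The full 18-month recruitment period matches both the 102 recruits and the 300 men approached.
2. Keep eligible men as the denominator, as the analysis section has it, and reword the Sample size section so that the 300 are eligible men.
3. If 12 months is kept for the proportion, restate the power for the number of men expected in that window and give the assumption behind that number.
4. Add recruits per open centre-month, with a 95% CI, to Analysis of primary endpoint. Make it the primary analysis if accrual is what the Primary Endpoint section means, and a supporting analysis otherwise. It supplies the pace needed to plan centres for 800 men in 48 months.

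The cost is SAP wording and one calculation from the logs and centre opening dates. No extra patients are needed. If 12 months is kept for the proportion, the stated power becomes less favourable. The wording should be settled before the recruitment logs are analysed.

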# Secondary Endpoints

The secondary endpoints involve measures of disease progression from baseline to 12 months, assessed by serial multi-parametric magnetic resonance imaging (MRI) of the prostate, serum PSA measurement, and prostate biopsy.

## Disease progression by MRI

Disease progression by MRI of the prostate will be defined as an increase in lesion volume of  $\geq$ 33% or an upgrading of MRI stage of disease to  $\geq$ T3. Disease regression by MRI will be defined as a decrease in lesion volume of  $\geq$ 33% or the absence of a lesion at 12 months where one was detected at baseline. In the case where no lesion was identified by MRI screening, disease progression will be defined as the development of a lesion of 0.2cc or greater and being assigned a PIRADS score of 4 or 5.

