#### 1. Change in tumour volume

An ordinal logistic regression model using proportional odds will be run to assess the progression or regression of disease as assessed by the change in tumour volume by MRI from baseline to 12 months. The dependent variable will be coded according to percentage change.

DV code	Tumour volume percentage change (%)	Description
0	-100 ≤ x ≤ -33	Greater than 33% decrease in tumour volume
1	-33 < x ≤ 33	Absolute change less than 33% in tumour volume
2	x > 33	Greater than 33% increase in tumour volume

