#### 5. Disease **progression** by any measure

A final logistic regression model will be run to assess the effect of treatment on disease progression by any of the three measures (tumour volume, serum PSA, Gleason score). Disease progression will be coded as 1 if disease progression is observed for any of the three disease measures and 0 otherwise. A regression of disease — a decrease in disease measure — will be treated as "no progression".

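### The MRI endpoint has no new-lesion rule for men with a baseline lesion, does not say which lesion volume is measured, and sets no precedence between progression and regression

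*SAP*

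**What the plan says.** The SAP section *Disease progression by MRI* has three parts.

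- **Progression, general rule.** "Disease progression by MRI of the prostate will be defined as an increase in lesion volume of" at least 33%, "or an upgrading of MRI stage of disease to" T3 or above.
- **Regression.** "Disease regression by MRI will be defined as a decrease in lesion volume of" at least 33%, "or the absence of a lesion at 12 months where one was detected at baseline".
- **Men with no lesion at screening.** "In the case where no lesion was identified by MRI screening, disease progression will be defined as the development of a lesion of 0.2cc" or more that is also scored PIRADS 4 or 5.

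Three later sections use the MRI result.

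- *Overall disease progression* reports the proportions progressed and regressed by type, with MRI as one type.
- *1. Change in tumour volume* fits an ordinal model to "the change in tumour volume by MRI from baseline to 12 months", coded by percentage change alone.
- *5. Disease progression by any measure* models "disease progression by any of the three measures (tumour volume, serum PSA, Gleason score") and codes a decrease in a measure as not progressed.

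No section says whether lesion volume or tumour volume means the index lesion, each lesion or the sum. None says which label wins when a man meets criteria pointing both ways.

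**The concern.** The SAP treats a new lesion of at least 0.2cc with PIRADS 4 or 5 as progression in a man who had none. The same finding in a man who already had a lesion has no criterion of its own. It counts only if it happens to move an undefined volume by 33% or comes with a stage upgrade. Nothing prevents such a man from being labelled regressed if his first lesion has shrunk.

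Two things are at stake. The reported proportions of MRI progression and regression would mix men classified under unequal rules. And one scan could be given different labels by different analysts, possibly after the data have been seen.

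**Working it through.** **Inputs.** The thresholds (+33%, -33%, 0.2cc, PIRADS 4 or 5, T3) come from *Disease progression by MRI*. The SAP gives no lesion volumes, so those below are assumed for illustration. Every man in the table has one baseline lesion, a new PIRADS 5 lesion of at least 0.2cc at 12 months, and stage below T3. The SAP gives no figure of its own to reproduce here.

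**Formulas.** With baseline volume b, the same lesion at 12 months i, and new lesion n:
- index reading: x = 100(i - b)/b
- total reading: x = 100(i + n - b)/b

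Progressed if x is at least 33, regressed if x is at most -33, otherwise unchanged.

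| b to i (cc) | n (cc) | Index reading | Total reading |
|---|---|---|---|
| 2.0 to 2.0 | 0.5 | 0%, unchanged | (2.5 - 2.0)/2.0 = +25%, unchanged |
| 1.0 to 0.3 | 0.3 | -70%, regressed | (0.6 - 1.0)/1.0 = -40%, regressed |
| 0.5 to 0.5 | 0.5 | 0%, unchanged | (1.0 - 0.5)/0.5 = +100%, progressed |
| 1.0 to 0.6 | 0.5 | -40%, regressed | (1.1 - 1.0)/1.0 = +10%, unchanged |
| 0.5 to 0 | 0.7 | -100%, regressed | (0.7 - 0.5)/0.5 = +40%, progressed |

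Each of these new lesions would be progression in a man with no lesion at screening. In the first two rows it is not progression under either reading, and in the second row the man is labelled regressed. In the last three rows the label depends on the reading; in the last it goes from regressed to progressed.

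**How far the total reading helps.** With a stable baseline lesion, a new lesion counts only if n/b is at least 0.33, that is b no larger than n/0.33. For n = 0.2cc the limit is 0.2/0.33 = 0.61cc. Beside a larger stable lesion, a new 0.2cc lesion does not count.

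**Conflict that does not depend on the volume reading.** Take a man with a single lesion that shrinks from 1.0cc to 0.6cc (-40%) while his MRI stage rises to T3.
- *Disease progression by MRI*: he meets both the progression and the regression definitions.
- *Overall disease progression*: he can be counted in both proportions.
- *1. Change in tumour volume*: he takes the lowest category, because only volume change is coded.
- *5. Disease progression by any measure*: the MRI component is named as tumour volume, so on that wording his decrease is not progression, although the MRI definition calls him progressed.

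**New lesions in the models.** The coding in model 1 has no place for a new-lesion event. For a man with no baseline lesion, percentage change has a zero denominator, so his progression under the MRI definition cannot be carried into model 1 as written.

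**The case against.** The strongest reply is that the rule need not exclude new lesions. Any man progresses on an upgrade to T3, and tumour volume can fairly be read as total burden. On that reading a stable 0.5cc lesion plus a new 0.4cc lesion is (0.9 - 0.5)/0.5 = +80%, which is progression. This stands. A reader might infer that a man with a baseline lesion and a new PIRADS 5 lesion is never a progressor, and the SAP does not support that. But the total reading does not close the gap, as the first two rows of the table show.

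Second, the volume measure may be set in the protocol or imaging instructions, which are not at hand. That is a fair reason not to rest the point on the missing definition alone. The restriction of the new-lesion criterion and the lack of precedence, however, lie in the SAP's own stated rule.

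Third, absence of a lesion may mean no lesion anywhere on the scan, so a man with a new lesion would not qualify. That is possible, but the fall from 1.0cc to 0.3cc reaches regression by volume and does not use that clause.

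Fourth, progression and regression are reported as separate proportions, so a man in both breaks neither. This is true of each proportion taken alone. It does not settle which label he carries or remove the mismatch with model 5.

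Finally, a size and PIRADS floor for new lesions beside a relative threshold for known ones is a coherent choice. It is not counted here as an error.

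**Conclusion.** The point holds. For men with a baseline lesion and a new qualifying lesion, the SAP's MRI rule can return unchanged or regressed under either volume reading, and for others the label turns on a reading the SAP does not fix. Shrinkage with an upgrade to T3 satisfies both definitions whatever volume is used.

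Whether a given man is misclassified depends on his volumes, his stage and the reading chosen. The volumes used here are illustrative. The SAP gives no lesion volumes and no frequency of new lesions beside old ones, so the share of progressors missed cannot be computed and none is claimed.

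A reader might also infer harm to the feasibility conclusion or to the size of the definitive trial. The SAP does not support that: the primary endpoint is recruitment, the 800-man figure is already stated, and no section carries an MRI event rate forward. The effect is limited to a secondary endpoint and the composite built on it. It is worth correcting because the remedy is specific and cheap.

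**What to change.** In *Disease progression by MRI*:
1. Apply the existing criterion (new lesion of at least 0.2cc, PIRADS 4 or 5) to all men, whether or not they had a lesion at screening.
2. State that progression by volume, new lesion or stage overrides regression, and that regression requires no new qualifying lesion.
3. State which volume is measured (index lesion or total) and how several baseline lesions are handled.

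Then use the same MRI status in *Overall disease progression* and in model 5. For model 1, either code its three categories from that status, or label it as a volume-only outcome and say how men without a baseline lesion are treated.

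Under items 1 and 2 every man in the table becomes a progressor under both volume readings, and the man with shrinkage and an upgrade to T3 has a single label.

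The cost is SAP wording and one derivation rule, with no extra scans. This assumes that the 12-month reads record the volume and PIRADS score of new lesions in men who already had one; if they do not, stored scans would need a further read. The rule should be fixed before outcome data are examined by arm.

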## Biochemical disease progression

Biochemical disease progression (or regression) will be defined as a 50% increase (or decrease) in serum PSA at 12 months from baseline.

## Histological disease progression

### Change in Gleason score

Histological disease progression/regression will be defined as an increase/decrease in Gleason score or primary grade upon repeat prostate biopsy. Examples:

- Gleason score 6 to 7 (increase in overall score)
- Gleason score 8 to 7 (disease regression, decrease in overall score)
- Gleason 3+4 to 4+3 (both score 7, increase in primary grade)
- Gleason 4+3 to 3+4 (disease regression, decrease in primary grade)

## Change in maximum cancer core length (MCCL)

Disease progression/regression will also be defined as a 50% increase/decrease in maximum cancer core length

## Serum hormone levels

Levels of serum testosterone, Follicle Stimulating Hormone (FSH), and Luteinizing Hormone (LH) will be measured every 6 months. Analyses will focus on whether serum levels have an effect on disease progression, and whether the serum concentrations differ between treatment arms.

### Cell Cycle Progression (CCP) Score

Biopsy samples taken pre-study and at 12 months will be used for CCP score analysis. Exploratory analyses will investigate how the change in CCP score differs between treatment arms and whether CCP score has an effect on disease progression.

## Pathology review

A minimum 10% sample of all prostate biopsy tissue received will undergo a central pathology review by the collaborating study pathologist at Centre for Molecular Oncology, Barts Cancer Institute, to ensure consistency of reporting.

#### Serum vitamin D3 and calcium

Levels of serum vitamin D3 and serum calcium will be measured at baseline, 6, 12, and 18 months. Hypercalcaemia (corrected serum calcium > 2.65mmol/L) is a well-known symptom of chronic vitamin D3 overdose.

## Study period and visits

The study will last for 18 months (plus ≥30 days for pharmacovigilance). Data will be collected at 3-monthly intervals. Secondary endpoint measures will be carried out at the following times:

- MRI taken at baseline and 12 months
- Prostate biopsy at baseline and 12 months for pathology review & CCP score analysis.
- Serum PSA measured at baseline and every 3 months until 18 months
- Serum testosterone, FSH, and LH at baseline and every 6 months until 18 months
- Serum vitamin D3 taken at baseline and every 6 months until 18 months
- Serum calcium at screening and 6, 12, and 18 months

## Demographics and clinical variables

Summary statistics for the baseline and follow-up demographics and clinical variables will be presented, both overall and by treatment arm, focusing on:

- Age
- BMI
- Serum PSA
- Gleason score
- Cancer of the Prostate Risk Assessment (CAPRA) score

The CAPRA scoring system was developed by the University of California, San Francisco and takes into account age, PSA, Gleason score, clinical stage, and percentage of positive cancer cores.

